3.3 Phase II

the GXT.

Phase II is designed to test flow rate effects on individual exercises & regimen overall SWPF values. This phase will include the 25 evaluable subjects from Phase I if they are interested in continued participation. If subjects from Phase I decline or are no longer eligible, additional subjects may be consented and screened for recruitment utilizing the modified screening requirements from Phase I (Appendix A, Study Calendar 1). Phase II will use the exercise regimen (Table 3.) and work rates determined in Phase I, with eight different PAPR models and two flow rates for each PAPR. Subject's will complete one 30-minute regimen = ten, 3 minute exercises completed in sequential order from light to hard work rates with breaks following the hard exercises (see Section 3.2) for sequence. 25 subjects x 8 PAPR models x 2 flow rates x 2 regimen replicates = 800 overall SWPF values (based on 10 exercises). Three Way Repeated Measures ANOVA will be used to analyze the data.

Each subject will come in to test 2 PAPRs and 2 flow rates per visit for approximately 3 hours, 392 for a total of 4 visits (~12 total hours) to complete the first replicate of tests. The subjects will 393 repeat the same procedure for the second replicate, meaning each subject will complete Phase II 394 over the course of 8 visits of approximately 3 hours per visit (~24 total hours). It is estimated that this phase will take 6 to 9 months (November 2019-July 2020). 396

PAPR Models

391

395

397

398

399

400

401

402

403

404

405 406

407

408 409

410

Eight PAPR models (4 PAPRs with loose-fitting hoods, 2 loose-fitting facepiece PAPRs with helmets, and 2 tight-fitting PAPRs) were selected for this study (Table 5.). The models were selected based on: 1) prevalence of respirators in healthcare (Wizner, 2016) and 2) their commercial availability. The assigned protection factors for each PAPR is 25 or 1000. Tight fitting full facepieces (models 1-2) have a tight seal along the chin and sides of face. Loosefitting full hoods (models 3-6) have a shroud covering the shoulders down to the mid-torso. Loose-fitting facepieces (models 7-8) have a cuff that loosely contacts the chin and the sides of the face. Each PAPR device weight will be measured and recorded. All PAPR devices used in this study will be set at the same airflow rate. Each subject will be asked to complete the comfort survey after each PAPR tested with all three flow rates in Phase II (Appendix M).

Table 5. Phase II PAPR Models

#	PAPR MODEL	OSHA APF	RIC DESIGN
			tight-fitting full
1	Bullard EVA	1000	facepiece
	2504.00	1000	tight-fitting full
2	MSA OptimAir	1000	facepiece
3	3M Versaflo		
	hood (S-403L (M/L size)	1000	loose-fitting full hood
	hood (S-403S (S/M size)	1000	
4	ILC Dover Sentinel XL		
	S-2019-10 (one-size)	1000	loose-fitting full hood
5	Bullard EVA		
	20TIC hood (one-size)	1000	loose-fitting full hood
6	Maxair Helmet CAPR w/ HE filter (Bio-Medical Devices, Inc.)		
	2261-01ML	25	loose-fitting full hood
	2261-01SM	25	
7	Maxair Helmet CAPR w/ HE filter (Bio-Medical Devices, Inc.)	25	loose-fitting facepiece

[figure not shown]

	3M VersaFlow w/ S133 cuff		
8	facepiece	25	loose-fitting facepiece

Flow Rates

 The two PAPR airflow rates tested in Phase II include: 1) 170 L/min for loose-fitting PAPRs and 115 L/min for tight-fitting PAPRs (based on the current NIOSH minimum certification airflow rates) and 2) 125 L/min for loose-fitting PAPRs and 100 L/min for tight-fitting PAPRs (experimental airflow rates below the NIOSH certification requirement). Flow rates at and below the NIOSH certification minimum, PAPRs will be modified and therefore not NIOSH certified. Modifications to these devices will reduce airflow by one of two ways as determined by the study team: 1) controlling voltage to the PAPR motor, 2) installing a 3-way valve into the blower hose (if equipped) to bleed-off excess flow (Figure 3).

Figure 3. Subject Wearing a PAPR with Fixed Airflow Valve

Simulated Workplace Protection Factor

SWPF testing will take place in both Phase II and Phase III, following the work rate determination in Phase I. Test subjects wearing PAPR will enter the test chamber and complete the exercise regimen (Table 3.) against a corn oil challenge aerosol.

For this test, a TSI Rear Light Scattering Laser Photometer, model 8587A, will be used to measure aerosol concentration inside of the respirators. A TSI model 8520, Dustrak Aerosol Monitor will be used to monitor chamber particle concentrations. Data collected by the laser photometer will be recorded on the NIOSH Dynamic Fit Software. Data will be analyzed using a three-way repeated measures ANOVA with subject number, model, and work rate, and the log transformed SWPF of each test as the dependent variable. The relative importance of each variable to PAPR performance will be determined. The SWPF will be calculated in two steps as follows:

1. Ratio of the Upstream and Downstream Particle Concentrations

$$SWPF_{i} = \frac{C_{out}}{C_{in}}$$

 Where: SWPF = simulated workplace protection factor; i = exercise number; $C_{out} = exercise$ upstream particle concentration; $C_{in} = exercise$ downstream particle concentration

2. Overall SWPF for Each PAPR Model

$$Overall SWPF = \frac{n}{\frac{1}{SWPF_1} + \frac{1}{SWPF_2} + \cdots + \frac{1}{SWPF_{n-1}} + \frac{1}{SWPF_n}}$$

Where: $SWPF_n = simulated$ workplace protection factor for a given exercise; n = number of exercises used during an SWPF test.

Test Chamber

The SWPF testing will be conducted inside a 16' x 16' x 10' charged corn oil test chamber in Building 40 of the National Personal Protective Technology Laboratory in Pittsburgh, PA. SWPF test setups are displayed in Figures 4A and 4B.

A 99% stock corn oil (CAS #8001-30-7) with the commercial product names Maise/Maize, Maydol, and/or Mazola oil will be used for test aerosol. It will be aerosolized using an MSP Model 2045 High Output Aerosol Generator capable of maintaining 5 to 100 mg/m³ of corn oil challenge aerosol concentrations for the required test duration. For SWPF testing, the test chamber will be maintained at ~20-40 mg/m³. The output aerosol will be dried with 30% dilution air, followed by neutralization with a Kr-85 charging source before entering into the exposure testing chamber. The aerosol will have a Mass Median Aerodynamic Diameter (MMAD) of 0.4 to 0.6 μ m, with a geometric standard deviation of less than 2.0. This size distribution will be measured once daily using a Scanning Mobility Particle Sizer (SMPS) system. This system is comprised of the TSI model 3080 Electrostatic Classifier, TSI model 3775 Condensation Particle Counter, and 3081 Long Differential Mobility Analyzer (DMA).

The aerosol in the exposure chamber will be mixed using four internal fans positioned in the top four corners of the charged corn oil test chamber, and the chamber conditions will be tracked by a humidity/temperature sensor. Corn oil aerosol particles will be continuously dispersed into the chamber, while an open exhaust port will remove excess air and maintain neutral pressure.

Figure. 4A: Aerosol Chamber Testing System for Loose-Fitting PAPRs

[figure not shown]
[figure not shown]

Figure. 4B: Aerosol Chamber Testing System for Tight-Fitting PAPRs

Subject Monitoring

During testing subjects will be equipped with a fingertip-pulse oximeter (AG Industries, St. Louis, MO) to monitor oxygen saturation information during testing. If the subject's O₂ saturation level goes below 90%, the test will be terminated. Subjects will also be equipped with a differential pressure line and a CO₂ line for monitoring CO₂ accumulation in the RIC. A CO₂ gas analyzer (CD-3A carbon dioxide analyzer and S-3A/I oxygen analyzer, AEI Technologies, Chicago, IL (or equivalent) will be used to continuously monitor CO₂ gas (percentage by volume) inside the PAPR facepiece during SWPF testing. The PAPR facepiece will be fitted with a sampling probe; flexible tubing will transport the in-mask sample to the CO₂ analyzer which will be located outside of the corn oil chamber.

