2.2 Secondary Objectives

- a. Assess PAPR usability and comfortability at varying work and flow rate conditions
- b. Understand the relationship between PAPR RIC design and SWPF

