Test subjects wearing the PAPRs will enter the chamber and perform two different exercise regimens (Table 6.). SWPF testing and chamber set up will be the same as during Phase II (Section 3.3). Laser photometer and Dustrak will be used to measure aerosol concentration inside and outside of the respirator, respectively. The SWPF for all particle sizes (10–1,000 nm) inside and outside the respirator will be determined. Each subject will be asked to complete the comfort survey after each PAPR tested in Phase III (Appendix N).

Table 6. Phase III Exercise Regimens

Exercise regime	Exercise #	Test exercise	Approximate Duration (min)	Hypothesized Work Rate
A	2	Reading: read the rainbow passage while standing	5	Light
	6	Reaching up and stepping out (Modified jumping jack): bending the left knee slightly while reaching up both arms overhead & looking up and stepping the right leg out to the side, then repeat with the other leg, at a rate of 10-12 sets/min.	5	Moderate
	9	Perform CPR/AED: perform CPR on a training manikin by compressing chest cavity ~1.5 - 2	5	Hard

		inches at a rate of 80-100 compressions/min. 2 minutes of CPR followed by 1 min AED, followed by 2 more minutes of CPR							
Minimum of 10 minute break in between regimens and vital signs return to within baseline limits									
В	3	Moving head side-to-side: moving head side-to-side at approximately 10 times/min while standing	5	Light					
	7	Walk on a treadmill: walking upright on a treadmill at a speed of 3 mile/h without movement of the head, and without speech.	5	Moderate					
	10	Stair climbing: Stair climbing (using a 3-step ladder) climb rate ~ 10-12 cycles/min (one cycle = up 3 steps and back down 3 steps).	5	Hard					

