⁶Replicates 1, 2, & 3 each include one 30-minute exercise regimen completed by the subject while monitored with a metabolic cart.

⁷Prior to each study visits exercise regimen test, subjects and a U.S. licensed health professional must complete the NPPTL Pre Visit Medical Evaluation form (Appendix L)

⁸After the subject completes the exercise regimen, they must be given a minimum of a ten-minute break before post visit medical evaluation (Appendix O) and a U.S. licensed health professional must review their pre and post test medical evaluations (Appendices M. & P) and approve discharge before they are dismissed from the visit.

After 25 evaluable subjects complete replicate 1 study interventions, an interim data analysis will be completed. If additional attempts for all subjects are found to be warranted for (replicate 2 and/or 3), subjects may return and complete replicate 2 and replicate 3 during the same visit. If this occurs then subjects must be given a minimum of a ten-minute break in between attempts, and their vital signs must be assessed and returned to baseline values prior to initiating third attempt.

¹⁰Documentation of General Photo release agreement or decline must be recorded for each subject (Appendix U)

2. Phase II Study Calendar 1492

Visit #1 ^{1,4} (3 hours)	Visit #2 ⁴ (3 hours)	Visit #3 ⁴ (3 hours)
Pregnancy Test ²	Pregnancy Test ²	Pregnancy Test ²
NPPTL Pre Visit Medical Evaluation ³	NPPTL Pre Visit Medical Evaluation ³	NPPTL Pre Visit Medical Evaluation ³
Model 1: Flow Rate 1 & 2 Exercise Regimen (Table 3): Replicate 1	Model 3: Flow Rate 1 & 2 Exercise Regimen (Table 3): Replicate 1	Model 5: Flow Rate 1 & 2 Exercise Regimen (Table 3): Replicate 1
Phase II Survey	Phase II Survey	Phase II Survey
Model 2: Flow Rate 1 & 2 Exercise Regimen (Table 3): Replicate 1	Model 4: Flow Rate 1 & 2 Exercise Regimen (Table 3): Replicate 1	Model 6: Flow Rate 1 & 2 Exercise Regimen (Table 3): Replicate 1
Phase II Survey	Phase II Survey	Phase II Survey
NPPTL Post Visit Medical Evaluation ⁵	NPPTL Post Visit Medical Evaluation ⁵	NPPTL Post Visit Medical Evaluation ⁵

Visit #4 ⁴ (3 hours)	Visit #5 ⁶ (3 hours)	Visit #6 ⁶ (3 hours)
Pregnancy Test ²	Pregnancy Test ²	Pregnancy Test ²
NPPTL Pre Visit Medical Evaluation ³	NPPTL Pre Visit Medical Evaluation ³	NPPTL Pre Visit Medical Evaluation ³

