rate comparisons and model comfort upon test end for each model. After each 30-minute exercise regimen completed subjects must be given a minimum of a 10-minute break and vitals must be assessed and returned to baseline prior to initiating next exercise regimen, even if for the same model.

⁵Subjects must be given a minimum of a ten-minute break before NPPTL Post Visit Medical Evaluation (Appendix O) completed and a U.S. licensed health professional must review both pre and post test medical evaluations (Appendices L & O) before they are dismissed.

⁶Replicate 2 study interventions should be completed in 4 additional visits. Each visit, the subject will complete the 30-minute exercise regimen for two PAPR models and 2 flow rates, for a total of 4 30-min tests. They must also complete a Phase II survey (Appendix M) for flow rate comparisons and model comfort upon test end for each model. After each 30-minute exercise regimen completed subjects must be given a minimum of a 10-minute break and vitals must be assessed and returned to baseline prior to initiating next exercise regimen, even if for the same model.

3. Phase III Study Calendar

Visit #1 ^{1,4} (3 hours)	Visit #2 ⁴ (3 hours)
Pregnancy Test ²	Pregnancy Test ²
NPPTL Pre Visit Medical Evaluation ³	NPPTL Pre Visit Medical Evaluation ³
Model 1: Exercise Regimen A & B (Table 6) - Replicate 1	Model 5: Exercise Regimen A & B (Table 6) - Replicate 1
Phase III Survey	Phase III Survey
Model 2: Exercise Regimen A & B (Table 6) - Replicate 1	Model 6: Exercise Regimen A & B (Table 6) - Replicate 1
Phase III Survey	Phase III Survey
Model 3: Exercise Regimen A & B (Table 6) - Replicate 1	Model 7: Exercise Regimen A & B (Table 6) - Replicate 1
Phase III Survey	Phase III Survey
Model 4: Exercise Regimen A & B (Table 6) - Replicate 1	Model 8: Exercise Regimen A & B (Table 6) - Replicate 1
Phase III Survey	Phase III Survey
NPPTL Post Visit Medical Evaluation ⁵	NPPTL Post Visit Medical Evaluation ⁵
·	Interim Data Analysis

Visit #3 ^{1,4} (3 hours)	Visit #4 ⁴ (3 hours)
Pregnancy Test ²	Pregnancy Test ²
NPPTL Pre Visit Medical Evaluation ³	NPPTL Pre Visit Medical Evaluation ³
Model 1: Exercise Regimen A & B (Table 6) - Replicate 2	Model 5: Exercise Regimen A & B (Table 6) - Replicate 2
Phase III Survey	Phase III Survey
Model 2: Exercise Regimen A & B (Table 6) - Replicate 2	Model 6: Exercise Regimen A & B (Table 6) - Replicate 2
Phase III Survey	Phase III Survey

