Model 3: Exercise Regimen A & B (Table 6) - Replicate 2	Model 7: Exercise Regimen A & B (Table 6) - Replicate 2
Phase III Survey	Phase III Survey
Model 4: Exercise Regimen A & B (Table 6) - Replicate 2	Model 8: Exercise Regimen A & B (Table 6) - Replicate 2
Phase III Survey	Phase III Survey
NPPTL Post Visit Medical Evaluation ⁵	NPPTL Post Visit Medical Evaluation ⁵

¹Subjects that participated in Phase I must complete consent and screening for Phase II prior to registration if it has been more than a year since their Phase I registration. Rescreening may also be completed within one year, if changes to subject's health and body measurements noted during a study visit (see section 3.1).

² Women of child bearing potential are required to complete a pregnancy test prior to each visit study interventions, which will be reviewed by a U.S. licensed health professional. Only one pregnancy test per 7 calendar days is required and study visits within the same 7 calendar days may waive additional pregnancy tests after first visit in that 7-day period.

³Prior to beginning study interventions at each study visit, subjects and a U.S. licensed health professional must complete the Pre Visit Medical Evaluation form (Appendix L)

⁴Subjects will complete exercise regimens A & B for 4 PAPR models per visit (~3 hours), for a total of four 30-min tests. After the subject completes exercise regimen A, they must receive a minimum of a ten-minute break and vitals must be assessed and have returned to baseline prior to initiating Exercise Regimen B. Subjects must also be provided a minimum of a ten-minute break and vitals must be assessed and have returned to baseline prior to initiating the next models exercise regimen A & B test. Additionally a Phase III Survey (Appendix N) must be completed by the subject at the end of each model tested (four per visit).

⁵Subjects must be given a minimum of a ten-minute break before post visit medical evaluation completed and a U.S. licensed health professional must review their pre and post test medical evaluations (Appendices M & P) before they are dismissed from the visit.

Volunteers Needed in Research Study

Superior Powered Air-purifying Respirator Tests and New Technologies (SPARTAN)

Powered Air-purifying Respirator

study volunteers to participate in research to help improve respirators for use by healthcare workers. This study will be conducted by the National Personal Protective Technology Laboratory (NPPTL) at NIOSH.

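### Comfort is surveyed once per PAPR model, so the schedule as written gives no comfort contrast by flow rate (where Appendix M contradicts it) or by work rate

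*Protocol*

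**What the plan says.** Section 2.2 sets secondary objective (a): "Assess PAPR usability and comfortability at varying work and flow rate conditions".

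**Phase II.** Section 3.3 counts the tests as "25 subjects x 8 PAPR models x 2 flow rates x 2 regimen replicates = 800 overall SWPF values (based on 10 exercises". On the survey it says "Each subject will be asked to complete the comfort survey after each PAPR tested with all three flow rates in Phase II (Appendix M". In the Phase II calendar of Appendix A, a block such as "Model 1: Flow Rate 1 & 2 Exercise Regimen (Table 3): Replicate 1" is followed by a single survey row, and this repeats for every model and both replicates. Note 4 to that calendar says "They must also complete a Phase II survey (Appendix M) for flow rate comparisons and model comfort upon test end for each model", and note 6 says the same for the second replicate.

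Appendix M is titled as an assessment of the flow-rate effect. Its header has a field for an airflow rate setting. Below that are six ratings, among them airflow, noise and an overall judgement. Each is an absolute rating; none compares one flow with the other.

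**Phase III.** Section 3.4 says "Each subject will be asked to complete the comfort survey after each PAPR tested in Phase III (Appendix N". Note 4 to the Phase III calendar adds "Additionally a Phase III Survey (Appendix N) must be completed by the subject at the end of each model tested (four per visit". Table 6 gives regimens A and B one light, one moderate and one hard exercise each, at five minutes per exercise. Flow is held at the NIOSH minimum. The Appendix N header has a field for the exercise regime but none for work rate.

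**The concern.** A rating can inform a flow or work-rate comparison only if it belongs to one level of that factor, or explicitly compares levels. On the written schedule, each Phase II form covers both flow rates and each Phase III form covers all three work rates. No analysis plan can recover ratings that were never collected by condition.

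The case for a lower flow rests partly on quieter and lighter devices that healthcare workers will tolerate. The airflow and noise items are where the study could show whether users notice a difference. If the forms are collected as scheduled, that evidence will not exist for the reduced flow, and secondary objective (a) will be met only as a comparison between models.

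**Working it through.** **Inputs.** 25 subjects, 8 models, 2 flow rates and 2 replicates (Section 3.3). Two surveys per visit over 8 visits in Phase II, and four per visit over 4 visits in Phase III (Appendix A). One light, one moderate and one hard exercise per regimen (Table 6).

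**The plan's own figure.** Phase II tests: 25 × 8 × 2 × 2 = 800, as Section 3.3 states.

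**Phase II forms as scheduled.** Per subject: 2 × 8 = 16. In total: 25 × 16 = 400. So there is one form for every pair of flow-rate tests.

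**Can a flow effect be estimated?** Take a linear model with an intercept (1), subjects (24), models (7) and replicate (1): 33 columns.

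| Phase II collection | Forms | Rank without flow | Rank with flow |
|---|---|---|---|
| One form per model, after both flows | 400 | 33 | 33 |
| One form per flow-rate test | 800 | 33 | 34 |

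In the first row every form carries the same half-and-half mix of flows. The flow column is therefore a constant and adds nothing. In the second row flow becomes estimable, with 25 × 8 × 2 = 400 within-subject, within-device pairs.

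**Phase III forms as scheduled.** Per subject: 4 × 4 = 16. In total: 25 × 16 = 400, against 25 × 8 × 2 regimens × 2 replicates = 800 regimen tests.

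**Can a work-rate effect be estimated?** With one form per model, every form covers the same six exercises, so no contrast exists. Now suppose one form per regimen (800 forms). The base model gains a regimen column, giving rank 34. Each regimen is one third light, one third moderate and one third hard, so the two work-rate columns are constants and the rank stays at 34. A rating per work-rate level is needed: 8 × 3 × 2 = 48 per subject, or 25 × 48 = 1,200 per item.

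**The case against.** The strongest reply concerns Phase II. Appendix M is titled for the flow-rate effect, its header carries an airflow setting, and the calendar notes give flow comparison as one purpose of the survey. A form with one setting field fits one form per setting. The notes fix when the survey is taken and do not say that a single form covers both flows, so two forms could be completed at that point. The header is also damaged in the text available, so its exact layout cannot be confirmed.

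Much of this stands. A form per flow rate may well have been intended, and if two were completed the flow contrast could be recovered. A reader might infer that the flow question is lost on any reading; the documents do not support that. They do show a conflict: Section 3.3, the calendar rows and the notes all point to one survey per model, and staff holding a one-setting form after two settings have no valid entry to make.

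Two other stronger readings fail:

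- A reader might infer that no comfort rating belongs to a single flow rate. Every Phase III rating does, because flow there is constant at the NIOSH minimum. What is missing is the contrast with the reduced flow. Phase II forms cannot supply it, since they mix both flows and differ in regimen, exercise duration and timing.
- A reader might infer that the reduced flow always comes last, so that recency biases the single rating. The calendar's numbering of the flow rates suggests a fixed order. The step in Section 5.3 on which flow is tested first breaks off before it settles the matter, and no rule is stated.

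The reply does not reach Phase III, where the calendar note fixes four forms per visit and both regimens mix all three work rates.

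**Conclusion.** The point holds, with different force in its two halves.

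- **Flow rate.** Schedule and form contradict each other. Following the schedule gives 400 forms for 800 tests and no within-device flow contrast.
- **Work rate.** 400 forms yield no contrast by work rate, and one form per regimen would not create one.

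Comfort by PAPR model remains answerable, and the primary SWPF objectives are untouched. The mention of three flow rates in Section 3.3 is a separate slip against the two-flow design.

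The counts assume 25 subjects completing every visit and two replicates per phase, as the calendars show. The Phase III count line in Section 3.4 names three replicates, which would give 25 × 8 × 3 = 600 forms with the same result. The equal mix of work rates within each regimen uses the hypothesised categories in Table 6, which Phase I may revise. With one form per model, reclassification changes nothing, because every form still covers the same six exercises.

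**What to change.** **Phase II.** Schedule one Appendix M form after each flow-rate test, with the operator recording the setting. Show this in Section 3.3, in the calendar rows and in notes 4 and 6 of Appendix A. Reword the reference to three flow rates in Section 3.3 to each of the two flow rates, and correct the same phrase in Section 8.2.

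**Phase III.** In Appendix N, ask the condition-dependent items (airflow, noise, overall) separately for light, moderate and hard exercise.

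**Cost.** One extra six-item form per model per visit: two per visit, 16 per subject, 400 in all. It fits in the break of at least ten minutes already required after every regimen, even for the same model, so no visit or chamber time is added. Appendix N grows from 6 ratings to 3 + 3 × 3 = 12.

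**Limits that remain.** If the flow order is fixed, as the calendar suggests but does not state, the paired flow contrast stays confounded with order and should be reported with that limit. Work rate has a similar limit: Section 7.4 describes exercises building from low to higher intensity, so ratings by work rate will also reflect time worn, and those for the lighter exercises will be given from memory.
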